Laryngoscope microsurgery (laryngomicrosurgery, LMS) is one of the most common otolaryngology procedures, mainly used to remove vocal cord polyps, nodules or cysts, laryngeal granuloma, or laryngeal papillomas, vocal cord plastic surgery, dipper-like Cartilage reduction, or fixation, etc. Traditional laryngoscope microsurgery requires general anesthesia for tracheal intubation, mainly because the endotracheal tube can provide a stable gas exchange airway. However, general anesthesia with endotracheal intubation requires the use of muscle relaxants, which may lead to the risk of postoperative pulmonary complications(1) and tracheal intubation may cause postoperative throat discomfort and pain (2,3)

Transnasal humidified rapid-insufflation ventilator exchange (THRIVE) is a physiological device that can provide heated 50-70L / min humidified oxygen. Cavity and provide a degree of continuous positive airway pressure.(4)

Since the development of the transnasal humidified rapid-insufflation ventilator exchange (THRIVE), because of the ability to provide an effective oxygen supply to patients without intubation anesthesia, many traditional intubation general anesthesia operations have to be performed without intubation (5) . The best way to use the nasal humidification rapid inflation exchange ventilation device is that the patient maintain self-breathing function and has a better gas exchange effect(6). If the patient is given a muscle relaxant or temporarily stopped breathing, it is difficult to completely avoid carbon dioxide retention and hypercapnia. (7,8)

Traditional laryngoscopy microsurgery requires endotracheal intubation anesthesia, which may lead to obstruction of the surgical field of vision and the inability to check the vocal cords completely. Transnasal humidified rapid-insufflation ventilator exchange (THRIVE) Optiflow can provide oxygenation to increase the success rate of laryngoscope microsurgery for non-intubation anesthesia patients (5), and Provide

excellent surgical vision and complete inspection of the vocal cords. Muscle relaxants are used during surgery to avoid reflexes such as coughing caused by vocal cords and throat irritation. The use of muscle relaxants during this time will cause the patient to apnea.

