Ho3: There is less sore throat in the nonintubation group than in the intubation group.

Ho4: Non-intubation and no muscle relaxation may lead to less postoperative pulmonary complications.

Ho5: In the non-intubation group, no muscle relaxants are more suitable for long-term surgery than those with muscle relaxants.

Statistical analysis (the statistical analysis tool will use IBM SPSS version 20):

- 1 、 The sample characteristic data will be expressed as average, SD, and median, and the category variables will be displayed in the form of count and percentage.
- 2 、 The 95% confidence interval will show the original data and the change from the baseline.
- 3 、 The difference between the three groups was analyzed using one-way ANOVA to analyze the comparison between the intubation and non-intubation groups for drug administration, the presence or absence of complications, the severity and

the degree of completion of the operation.

- 4 ‧ The differences between the groups will be evaluated by chi-square test or Fisher's exact test.
- 5 ‧ Unless otherwise stated, all statistical tests will be two-way and evaluated at a significance level of 0.05.

Sample size calculation :

The main purpose of the study will focus on the completion of surgery and the occurrence of complications. In order to obtain the total number of participants in the study, a sample size will be calculated to detect a difference in incidence reduction of 25%. A statistical power of 80%, a 5% alpha and up to 10% possible sample loss. Therefore, each group will require 30 patients (90 in total). Considering the number of patients undergoing laryngoscope microsurgery each year, we estimate that there may be a total of 45 patients within a year. After meeting the inclusion criteria and obtaining patient consent, 45 patients will be included in the treatment plan in the first year, and the remaining sample size will be completed next year.

Primary outcome(2nd year) :

- 1 ‧ Less carbon dioxide retention and less hypercapnia.
- 2 ‧ Reduce postoperative lung complications.

Statistics from 10/20/2020 to 5/11/2021 :

Table I-i. Baseline demographics

Variable	G1(n=11)		G2(n=7)		G3(n=11)		p-value
	Mean	SD	Mean	SD	Mean	SD	
Age	52.0	13.9	46.9	8.4	51.7	14.2	0.66
BMI	26.4	5.5	24.5	3.5	25.1	2.5	0.78

Table I-ii. Baseline demographics

Variable	G1(n=11)		G2(n=7)		G3(n=11)		p-value
	n	(%)	n	(%)	n	(%)	
Sex							
male	7.0	63.6	3.0	42.9	5.0	45.5	0.60
female	4.0	36.4	4.0	57.1	6.0	54.5	
ASA							

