ASA I	3.0	27.3	3.0	42.9	9.0	81.8	0.04
ASA II	8.0	72.7	4.0	57.1	1.0	9.1	
ASA III	0.0	0.0	0.0	0.0	1.0	9.1	
Medical history							
HTN	3.0	27.3	0.0	0.0	4.0	36.4	0.20
CVA	1.0	9.1	0.0	0.0	0.0	0.0	0.43
CVD	1.0	9.1	0.0	0.0	3.0	27.3	0.22
DM	1.0	9.1	0.0	0.0	2.0	18.2	0.46
Endocrine	1.0	9.1	2.0	28.6	1.0	9.1	0.43
Genitourinary	0.0	0.0	1.0	14.3	0.0	0.0	0.20
HPL	1.0	9.1	1.0	14.3	0.0	0.0	0.47
Neurologic	0.0	0.0	1.0	14.3	1.0	9.1	0.47
Hepatitis B	1.0	9.1	1.0	14.3	0.0	0.0	0.47

Table I-ii. During the acceptance period, group 3 included 1 ASA3 case, and the remaining groups have not yet encountered ASA3 cases.

Table II. Arterial blood oxygen changes during surgery

Variable	G1(n=11)		G2(n=7)		G3(n=11)		p-value
	Mean	SD	Mean	SD	Mean	SD	
Before surgery							
pH_1	7.4	0.0	7.3	0.0	7.4	0.0	0.34
PaCO2_1	49.5	2.5	53.6	9.5	51.3	6.5	0.58
PaO2_1	321.2	79.6	451.9	108.6	377.5	196.6	0.14
SO2_1	99.7	0.8	99.9	0.0	99.8	0.4	0.50
HCO3-_1	28.3	1.7	28.6	3.3	28.8	1.6	0.67
In surgery							
pH_2	7.3	0.0	7.2	0.1	7.3	0.0	0.00
PaCO2_2	54.4	7.6	86.4	21.7	55.5	10.8	0.00
PaO2_2	186.9	64.0	321.8	128.2	341.9	136.9	0.02
SO2_2	99.3	1.1	99.6	0.5	99.7	0.5	0.48
HCO3-_2	27.7	1.9	31.8	4.1	29.1	2.7	0.06
After surgery							
pH_3	7.4	0.0	7.4	0.1	7.4	0.0	0.07
PaCO2_3	43.6	4.0	45.1	9.0	43.3	5.7	0.78
PaO2_3	123.3	63.1	110.8	16.1	116.3	29.6	0.77
SO2_3	98.0	1.5	98.2	1.0	98.3	1.4	0.81
HCO3-_3	25.8	1.7	26.3	2.9	27.0	2.5	0.55

Table II. During the operation, the PaCO2 value of the second group was >80mmHg.

Table III. Discomfort after surgery

Variable	G1(n=11)		G2(n=7)		G3(n=11)		p-value
	n	(%)	n	(%)	n	(%)	
Sore throat	3.0	27.3	0.0	0.0	4.0	36.4	0.20
Hoarseness	6.0	54.5	6.0	85.7	7.0	63.6	0.39
Difficulty breathing	0.0	0.0	0.0	0.0	1.0	9.1	0.43

Table III. One case in group 3 reported dyspnea in the recovery room. In most cases of laryngoscope surgery, the voice is required to be silenced after the operation, so the case cannot make a sound.

Table IV. Side effects after surgery

Variable	G1(n=11)		G2(n=7)		G3(n=11)		p-value
	n	(%)	n	(%)	n	(%)	
nausea	0.0	0.0	0.0	0.0	1.0	9.1	0.43
Vomiting	1.0	9.1	0.0	0.0	1.0	9.1	0.71
Nausea and vomiting	0.0	0.0	0.0	0.0	1.0	9.1	0.43

Table IV. One patient in group 1 had the side effect of vomiting.

In group 3, 1 case had nausea and vomiting.

Table V. Three stages of vital signs

Variable	G1(n=11)		G2(n=7)		G3(n=11)		p-value
	Mean	SD	Mean	SD	Mean	SD	
Before surgery							
BT	36.0	0.5	36.3	0.4	36.2	0.5	0.61
SpO2	98.8	1.3	98.1	1.5	97.7	2.1	0.46
NBPs	136.5	11.2	121.7	7.5	124.0	18.5	0.04

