Table VII. The surgeon was satisfied with the surgical satisfaction of the three groups, but the stress intensity was higher when performing non-intubation and nerve block surgery.

Table VIII. Dunnett T3 Post-hoc tests of during the operation

variable			M.D (I-J)	SE	p-value
pH_2	G1	G2	.135961*	.024404	.001
		G3	-.013455	.017469	.825
	G2	G1	-.135961*	.024404	.001
		G3	-.149416*	.024411	.000
	G3	G1	.013455	.017469	.825
		G2	.149416*	.024411	.000
PaCO2_2	G1	G2	-32.0468*	8.5162	.020
		G3	-1.1636	3.9766	.987
	G2	G1	32.0468*	8.5162	.020
		G3	30.8831*	8.8281	.023
	G3	G1	1.1636	3.9766	.987
		G2	-30.8831*	8.8281	.023
PaO2_2	G1	G2	-134.9130	52.1401	.087
		G3	-155.0273*	45.5545	.012
	G2	G1	134.9130	52.1401	.087
		G3	-20.1143	63.6399	.984
	G3	G1	155.0273*	45.5545	.012
		G2	20.1143	63.6399	.984

*. The M.D is significant at the 0.05 level.

[figure not shown]
Table VIII. Found the following situation :

1. In the non-intubated and muscle relaxant group (G2), the pH value during the operation was lower than the non-intubated and nerve-blocking group (G3), and lower than the normal value (7.35-7.45) .
2. During the operation, the PaCO2 of the non-intubated and muscle relaxant group (G2) was significantly higher than intubated group and also higher than the non-intubated and nerve-blocking group.
3. The PaO2 value of the intubation group (G1) during the operation was lower than that of the non-intubation group.

KSVGH20-C9-09 CASE REPORT

No:	Consent Signed _(MM/DD/YYYY) :	Operation Date:				
Patient status : _____						
Reason for quitting :						
Gender:	Age:	Weight _(kg) :	Height _(cm) :	BMI:	ASA:	
BASELINE MEDICAL/SURGICAL HISTORY :						
Time to enter the room :		Before induction BT:_____ SpO ₂ :_____ BP:___/___ PR:___ RR:___				
Study Group		Operation time				
Induction time		Anesthesia time				
Endo size & pressure		Propofol dose		Rocuronium dose		
		Fentanyl dose		Cisatracurium dose		
GAS		Before(:) G1: intubation ; G2: cis and scc ; G3: SLNB		OP end(:)		
pH				POR(:)		
PaCO ₂						
PaO ₂						
SO ₂ %						
HCO ₃ ⁻						
Time to post anesthesia recovery room :						
BT:_____ SpO ₂ :_____ BP:___/___ PR: ___ RR:_____						
PACU	Time	oxygen	respiration	circulation	consciousness	activity

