i:oxygen saturation 2: able to maintain oxygen saturation >92% on room air; 1: needed oxygen inhalation to maintain oxygen saturation >90%; 0: oxygen saturation <90% even with oxygen supplement ii:respiration 2: able to breathe deeply and cough freely; 1: dyspnea or limited breathing; 0: apneic iii:circulation 2: blood pressure ±20% of preanesthetic level; 1: blood pressure from ±20% to 49% of preanesthetic level; 0: blood pressure ±50% of preanesthetic level iv:consciousness 2: fully awake; 1: arousable on calling; 0: not responding v:activity 2: able to move 4 extremities voluntarily or on command; 1: able to move 2 extremities voluntarily or on command; 0: unable to move extremities voluntarily or on command						

Surgical records

	Ant.	Middle	Post.	Mixed	
Lesion site					
	Vocal polyp	Vocal cyst	Vocal atrophy	Vocal paralysis	Laryngeal tumor Bx
LMS Procedures					
Surgery completion	 Complete		 Partially complete		 Incomplete
Satisfaction	 Satisfied		 Partially satisfied		 Unsatisfied
Vision	 Good		 Poor		
Poor Visualization	 Inability to suppress gag reflex  Inability to achieve anesthesia  Had to change approach  Others:		 Copious secretions  Difficulty with vocal cord injection		
The Cormack-Lehane (CL) glottis view classification  I  IIa  IIb  III  IV					
					
Laryngeal compress :  Not applied  Applied					
Stress index  1  2  3  4  5					
Other :					

Postoperative evaluation

I. Evaluation (Score : none=1,minor=2,moderate=3,severe=4) , **time** :

- Sore throat : _____
- Hoarseness : _____
- Swallowing difficulty : _____
- Breathing difficulty : _____

II. Ward recording (24hr postoperative event) :

Score	Nausea()	Vomiting()	Nausea/vomiting()
0	none	none	none
1	minor	minor	minor
2	moderate	moderate	moderate
3	severe	severe	severe

D EXPECTED WORK ITEMS AND SPECIFIC RESULTS

Projects expected to be completed in the second year

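### Throat symptoms are scored only after surgery, and hoarseness mostly under voice rest, so the hoarseness comparison between anaesthetic groups cannot be interpreted

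*Protocol*

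**What the plan says.** Section C of the protocol reports interim data on 29 patients. Under "Table III. Discomfort after surgery" it gives counts, percentages and a p-value for three symptoms by anaesthetic group. The hoarseness row reads "Hoarseness 6.0 54.5 6.0 85.7 7.0 63.6 0.39". The table's footnote adds: "In most cases of laryngoscope surgery, the voice is required to be silenced after the operation, so the case cannot make a sound".

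The case report form places sore throat, hoarseness, swallowing difficulty and breathing difficulty under its postoperative evaluation, on one scale: "Score : none=1,minor=2,moderate=3,severe=4". The time of assessment is a blank to fill in. The preoperative part has a field headed "BASELINE MEDICAL/SURGICAL HISTORY" and vital signs, but no score for any of the four symptoms.

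Section B describes the operation as "mainly used to remove vocal cord polyps, nodules or cysts, laryngeal granuloma, or laryngeal papillomas", among other laryngeal procedures. The method summary says that patients are divided into three groups and describes no random allocation.

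**The concern.** A symptom that patients may already have before surgery says little about the anaesthetic when it is scored once, afterwards. Hoarseness is such a symptom in people with vocal cord lesions. The operation on the cords is a second possible cause, and voice rest makes the symptom hard to observe. If the groups also differ in their lesions, a difference in hoarseness can arise without any effect of the anaesthetic, and a real effect can be masked.

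Hoarseness itself is a secondary item. The same gap in the form, however, applies to sore throat, and Ho3 is a hypothesis about sore throat. No analysis plan can recover a preoperative score that was never collected, so the remedy has to be in the form while patients are still being recruited.

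**Working it through.** **Inputs.** Table III: hoarseness 6/11, 6/7, 7/11; sore throat 3/11, 0/7, 4/11; difficulty breathing 0/11, 0/7, 1/11. Table VI: procedures by group. Target 90 patients, 29 enrolled, so 90 − 29 = 61 remain.

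**1. The plan's own figure.** Overall hoarseness is (6 + 6 + 7)/29 = 19/29 = 65.5%. Expected counts under no difference:

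| | G1 | G2 | G3 |
|---|---|---|---|
| Hoarse | 11 × 19/29 = 7.21 | 7 × 19/29 = 4.59 | 7.21 |
| Not hoarse | 11 × 10/29 = 3.79 | 7 × 10/29 = 2.41 | 3.79 |

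Pearson chi-square = Σ(O − E)²/E = 0.202 + 0.436 + 0.006 + 0.384 + 0.828 + 0.011 = 1.867 on 2 df, p = 0.393. This reproduces the stated 0.39. Four of the six expected counts are below 5; the exact (Fisher-Freeman-Halton) test gives p = 0.54. Neither test shows a group difference.

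**2. Denominators against the footnote.** The denominators are the full 11, 7 and 11, so every patient was classed as hoarse or not hoarse. The footnote says that most such patients cannot use the voice. The form has no entry for this, so how silenced patients were scored is unknown.

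**3. What the counts allow.** Take the entries as correct. Without a preoperative score, hoarseness that is new after surgery lies anywhere in 0–6 of 11 (G1), 0–6 of 7 (G2) and 0–7 of 11 (G3). The difference G1 minus G2 in new hoarseness can then be anything from 0 − 6/7 = −85.7 to 6/11 − 0 = +54.5 percentage points.

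As an illustration only, assume that a share b of every group was hoarse before surgery and stayed so. The rate among the rest is (p − b)/(1 − b):

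| b (assumed) | G1 | G2 | G3 |
|---|---|---|---|
| 0% | 54.5% | 85.7% | 63.6% |
| 30% | 35.1% | 79.6% | 48.1% |
| 50% | 9.1% | 71.4% | 27.3% |

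A common b leaves the order of the groups unchanged but not the level. If b differs by group, the order is not fixed either.

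**4. Can balance be assumed?** Cyst plus atrophy cases: G1 4 + 1 = 5/11, G2 2 + 2 = 4/7, G3 0/11. Polyps: 1/11, 1/7, 3/11. Procedures classed as other: 4/11, 2/7, 8/11. The protocol's p-value for procedure mix is 0.14, which with 29 patients does not establish balance. With no random allocation described, there is no design reason to expect it.

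**The case against.** The strongest case against is that little depends on hoarseness. It is not in Ho1 to Ho5, it is neither the surgical completion score nor a second-year primary outcome, and the text summary of the interim results does not mention it. The protocol draws no conclusion from p = 0.39 and states the voice-rest caveat beside the table. The form also records medical history, procedure and lesion site. All of this stands and keeps the point minor. It does not supply a preoperative score, and it does not help sore throat, which is a named hypothesis.

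Three stronger readings are tempting, and the documents do not support them.

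- *Hoarseness reflects the disease and voice rest rather than the anaesthetic.* No preoperative rate is given. Voice rest did not automatically produce a positive entry, since 10 of 29 patients were recorded as not hoarse. G3 has no cyst or atrophy cases, yet 7/11 were hoarse against 6/11 in G1. The procedure mix shows only that balance cannot be assumed, not that disease explains the rates.
- *Hoarseness dominates the complication outcome.* The sample size section says: "The main purpose of the study will focus on the completion of surgery and the occurrence of complications". Hoarseness makes up 19 of the 7 + 19 + 1 = 27 entries in Table III. But the results summary reports the same 29 patients as free of complications, so hoarseness does not appear to be counted as one.
- *The plan promises a change score for these symptoms that it cannot deliver.* Item 2 of the statistical analysis says: "The 95% confidence interval will show the original data and the change from the baseline". It is generic and names no symptom; blood gases and vital signs, which do have a value before surgery, fit it.

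**Conclusion.** The point holds as a minor, cheap improvement to data collection. The hoarseness comparison in Table III cannot distinguish existing laryngeal disease, the operation, voice rest and the anaesthetic, and an anaesthetic contribution is neither shown nor excluded. The possible range of new hoarseness runs from none to every recorded case in each group. The p-value of 0.39 is correctly computed as a Pearson chi-square but tells the reader nothing about the technique.

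The conclusion rests on the form as printed being the one in use, and on allocation not being random, since none is described. It affects no primary outcome or sample size. Its wider relevance is sore throat under Ho3, which also lacks a preoperative score.

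**What to change.** For the remaining 61 patients:

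- score the same four items (1–4) before surgery;
- make the postoperative assessment at one fixed time, the same in all groups;
- add an entry *not assessable – voice rest* for hoarseness, and report its frequency by group;
- compare groups on the postoperative score adjusted for the preoperative score, or on new or worsened symptoms. Under the second option a patient who starts at 4 cannot worsen, so report how many do; the adjusted comparison avoids losing them.

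Hoarseness should stay in the comparison where it can be assessed, because it is a plausible harm of intubation. For the first 29 patients, keep the counts as descriptive, drop the p-value, and note that the groups cannot be compared on this item.

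The cost is four questions before surgery, one tick-box and a table note. The first 29 patients yield no usable hoarseness comparison. If many later patients are under voice rest at the chosen time, the item may remain descriptive for them too. A preoperative score also does not remove differences in the surgery performed, so the procedure mix should be shown alongside.

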If nonintubation anaesthesia for laryngomicrosurgery can be performed with nerve block and intravenous anesthetic medicine, the cardiovascular risks may decrease because of avoiding CO2 retention by maintaining patient's spontaneous breathing function. The feasibility and safety of nonintubated LMS with spontaneous breathing was evaluated in this case series.

Method

We divide the patients who need laryngoscopy microsurgery into three groups. The first group is general anesthesia with endotracheal tube intubation, the second group is non-intubation with muscle relaxant administered; the third group is non-intubation without muscle relaxant.

The three groups will perform arterial blood oxygen analysis (collecting PaO₂, PaCO₂, pH, HCO₃-data) before intubation, before muscle relaxant administration and before SLNB, after the operation and 15 minutes after transferring to the recovery room, as well as the pressure of the surgeons and the degree of completion of the operation to analyze the difference between intubated general anesthesia and non-intubation anesthesia.

Results

Last year, we passed the in-hospital plan (2021/04/07) and have been included (Table 1). There are 15 males and 14 females, all of whom have completed the trial phase without complications. Group 1 earns 11 people, Group 2 earns 7 people, and Group 3 earns 11 people.

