During the operation, a pulse oximeter will be used to monitor and record the patient's oxygen saturation. The patient's gender, height, weight, BMI, age, past medical history, ASA classification, type of laryngoscopic surgery, operation time, lesion location, blood loss, and anesthesia records will be kept.

All three groups of patients will use radial artery catheters. In addition, the three groups performed arterial blood gas analysis (including: PaO₂, PaCO₂, pH, HCO₃⁻) at the following times to understand the difference of pCO₂ in different groups and as a secondary result.

The first period to measure those variables is before each set of surgery are follows:

The first group is before tracheal intubation.

The second group was before the administration of muscle relaxants.

The third group is before applying superior laryngeal nerve block bilaterally.

The second period to measure those variables is the end of the operation.

The third period to measure those variables is 15 minutes after entering the recovery room.

All the anesthesia time, operation start time and operation end time of the three groups will be recorded, and the relationship between them will be discussed.

After the operation, the surgeon and the patient will be asked to do a questionnaire survey in order to understand whether the non-intubation anesthesia laryngoscope microsurgery of the self-breathing causes obstruction or other difficulties for the operator, as well as the patient's postoperative recovery, surgical satisfaction and operation After scoring. Finally, the surgeon's score on the degree of surgical completion was taken as the primary outcome.

Conditions for participating in this research project:

- Subjects are between 20-80 years old.
- Patients undergoing laryngoscope microsurgery.

- Anesthesiologists rated ASA as between I and III.

If those who are included have any of the following conditions, you will not be able to participate in this research project:

- Having drug dependence and drinking habits.
- Abnormal heart, liver and kidney function.
- Allergic reactions to narcotic drugs.
- Emergency surgery.
- pregnancy.
- Refuse to participate.

This study will explore the following assumptions:

Ho1: The intraoperative field of vision of the nonintubation group is clearer than that of the intubation group.

Ho2: Non-intubation and no muscle relaxation has less carbon dioxide retention and less hypercapnia.

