NBPd	83.8	9.7	83.3	9.1	71.6	14.5	0.06
PR	69.8	7.5	71.4	16.0	72.3	10.2	0.46
RR	14.7	2.9	15.6	4.0	15.8	2.6	0.79
In surgery							
SpO2	98.4	1.0	98.1	1.8	97.9	2.2	0.96
NBPs	128.7	19.7	133.3	16.2	123.8	16.4	0.45
NBPd	80.2	11.4	72.9	9.2	71.4	10.2	0.15
HR	83.8	15.1	90.4	9.6	88.4	13.3	0.54
After surgery							
BT	36.2	0.5	36.0	0.1	36.0	0.4	0.26
SpO2	98.9	1.4	98.9	1.1	98.3	2.3	0.85
NBPs	138.5	26.5	117.0	13.4	124.4	6.4	0.20
NBPd	85.5	16.8	77.3	14.8	78.0	8.5	0.26
PR	83.5	6.6	81.1	12.6	89.1	13.2	0.46
RR	15.4	3.0	16.1	4.0	15.8	2.8	0.63
PAR Score	8.8	1.7	7.1	2.1	7.8	2.1	0.15

Table V. The heartbeat of group 2 tends to rise during the operation

Table VI. Operation status

Variable	G1(n=11)		G2(n=7)		G3(n=11)		p-value
	Mean	SD	Mean	SD	Mean	SD	
OP time	77.4	35.8	37.3	8.1	39.7	21.4	0.00
	n	(%)	n	(%)	n	(%)	
LMS Procedures							
Vocal polyp	1.0	9.1	1.0	14.3	3.0	27.3	0.14
Vocal cyst	4.0	36.4	2.0	28.6	0.0	0.0	
Vocal atrophy	1.0	9.1	2.0	28.6	0.0	0.0	
Vocal paralysis	0.0	0.0	0.0	0.0	0.0	0.0	
Laryngeal tumor	1.0	9.1	0.0	0.0	0.0	0.0	
Other	4.0	36.4	2.0	28.6	8.0	72.7	
Lesion site							
Ant.	3.0	27.3	0.0	0.0	0.0	0.0	0.16
Middle	4.0	36.4	3.0	42.9	5.0	45.5	
Post.	1.0	9.1	0.0	0.0	2.0	18.2	
Mixed	1.0	9.1	0.0	0.0	0.0	0.0	
Ant & Middle	2.0	18.2	1.0	14.3	0.0	0.0	
other	0.0	0.0	3.0	42.9	4.0	36.4	
Surgery completion							
Complete	11.0	100.0	7.0	100.0	11.0	100.0	N/A
Partially complete	0.0	0.0	0.0	0.0	0.0	0.0	
Incomplete	0.0	0.0	0.0	0.0	0.0	0.0	
Vision							
Good	10.0	0.9	7.0	100.0	10.0	0.9	0.71
Poor	1.0	0.1	0.0	0.0	1.0	0.1	
Poor Visualization							
none	10.0	90.9	7.0	100.0	10.0	90.9	0.51
Difficulty with vocal cord injection	0.0	0.0	0.0	0.0	1.0	9.1	
Other	1.0	9.1	0.0	0.0	0.0	0.0	
The Cormack-Lehane (CL) glottis view classification							
I	9.0	81.8	6.0	85.7	9.0	81.8	0.97
IIa	2.0	18.2	1.0	14.3	2.0	18.2	
IIb	0.0	0.0	0.0	0.0	0.0	0.0	
III	0.0	0.0	0.0	0.0	0.0	0.0	
IV	0.0	0.0	0.0	0.0	0.0	0.0	
Laryngeal compress							
Not applied	1.0	9.1	0.0	0.0	0.0	0.0	0.43
Applied	10.0	90.9	7.0	100.0	11.0	100.0	
N/A : Not suitable for any statistics.							

Table VI. Among the three groups of operation time, the operation time of the first

group was longer than that of the other two groups.

Table VII. Surgeon's Feedback

Variable	G1(n=11)		G2(n=7)		G3(n=11)		p-value
	n	(%)	n	(%)	n	(%)	
Satisfaction							
Satisfied	11.0	100.0	7.0	100.0	10.0	90.9	0.43
Partially satisfied	0.0	0.0	0.0	0.0	1.0	9.1	
Unsatisfied	0.0	0.0	0.0	0.0	0.0	0.0	
	Mean	SD	Mean	SD	Mean	SD	
Stress index	1.0	0.0	1.9	1.2	2.0	0.8	0.01

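### Surgical completion is analysed only by tests for a group difference, which cannot support a feasibility conclusion when nearly every operation is complete

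*Protocol*

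**What the plan says.** **Aim.** The protocol's opening summary says: "The feasibility and safety of nonintubated LMS with spontaneous breathing was evaluated in this case series". In section C (Methods and Study Procedure), the postoperative questionnaire is meant to show "whether the non-intubation anesthesia laryngoscope microsurgery of the self-breathing causes obstruction or other difficulties for the operator".

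**Outcome.** The same paragraph of section C ends with the surgeon's "score on the degree of surgical completion was taken as the primary outcome". The case report form records completion as complete, partially complete or incomplete. The sample-size paragraph names completion and complications as the main focus. A separate list in section C then gives carbon dioxide retention and lung complications as the primary outcomes for the second year.

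**Analysis.**
- Item 2: "The 95% confidence interval will show the original data and the change from the baseline".
- Item 3: "The difference between the three groups was analyzed using one-way ANOVA". The degree of completion is among the variables listed there.
- Item 4: "The differences between the groups will be evaluated by chi-square test or" Fisher's exact test.
- Item 5: "all statistical tests will be two-way and evaluated at a significance level of 0.05".

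**Data so far.** Table VI shows completion of 11/11, 7/7 and 11/11 in groups 1, 2 and 3. The p-value column reads N/A, explained as "N/A : Not suitable for any statistics".

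**The concern.** A feasibility question about completion asks how large a shortfall the data still allow. A test for a difference does not answer that. A non-significant p-value does not show similarity, and with no failures in any arm the test carries no information. Table VI already shows this on the first 29 patients.

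Two results are at stake. If the remaining 61 operations are also complete, the outcome that section C calls primary has counts but no inferential conclusion. If a few operations fail, a non-significant p-value could be reported as no difference when the data allow a large shortfall.

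**Working it through.** **1. The plan's own figure.** The protocol gives a 25% difference, 80% power, 5% two-sided alpha and 10% loss, but no base rates. I assume 100% against 75% complete, with the pooled-variance formula:

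n = [1.960 × √(2 × 0.875 × 0.125) + 0.842 × √(0.75 × 0.25)]² / 0.25² = (0.917 + 0.364)² / 0.0625 ≈ 26.3, so 27 evaluable; 27 / 0.9 = 30 per group.

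This matches the stated 30. Moving away from 100% raises it: 95% against 70% needs 40 per group and 90% against 65% needs 48, after loss. The size is built to detect a difference of about 25 points, not to bound a small shortfall.

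**2. The planned tests when all 30 per group are complete.**
- ANOVA: between-group and within-group sums of squares are both zero, so F = 0/0.
- Chi-square: the expected counts for non-complete are zero, so the statistic is undefined.
- Fisher: only one table is possible with these margins, so p = 1.

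**3. The planned tests when some operations fail.** I count complete against not complete and compare one arm with 30/30. For five failures in 30, two-sided Fisher is p = 2 × C(30,5) / C(60,5) = 0.052. For six it is 0.024. An arm with 25/30 (83.3%) complete is therefore not significantly different at 0.05.

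**4. Intervals on the same data.**
- Exact (Clopper-Pearson) 95% lower limit with no failures: 0.025^(1/n). For 30/30 this is 88.4%. For the present data it is 71.5% (11/11) and 59.0% (7/7).
- Wilson lower limit for 30/30: 30 / (30 + 3.84) = 0.886.
- Newcombe lower limit for a difference d = p₁ - p₂: d - √[(p₁ - l₁)² + (u₂ - p₂)²], where l and u are the Wilson limits. Against a comparator at 30/30, u₂ - p₂ = 0.

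| Test arm (of 30) | Comparator | d (points) | p₁ - l₁ | Newcombe lower limit (points) | Fisher p |
|---|---|---|---|---|---|
| 30 | 30/30 | 0 | 1 - 0.8865 = 0.1135 | -11.4 | 1 |
| 29 | 30/30 | -3.3 | 0.9667 - 0.8333 = 0.1334 | -16.7 | 1 |
| 25 | 30/30 | -16.7 | 0.8333 - 0.6644 = 0.1690 | -33.6 | 0.052 |

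The upper limit in the first row is +11.4. With 27 evaluable per arm, all complete, the interval is -12.5 to +12.5. On the present data, group 3 minus group 1 is -25.9 to +25.9 and group 2 minus group 1 is -35.4 to +25.9.

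Fisher's p is 1 in both of the first two rows, although the shortfall that the data allow grows from 11.4 to 16.7 points.

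**The case against.** The strongest reply is that the protocol never asks whether completion is as good as with intubation. Ho1 to Ho5 do not mention completion, the sample size is for detecting a difference, and section D speaks of improving the success rate. This stands. A reader might infer that the trial is a non-inferiority trial lacking its margin. The documents do not support that: it is an inference from the feasibility aim and the operator-difficulty question, and no margin is stated anywhere.

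A reader might also infer that the outcome will yield no statistic at all. That goes too far. Item 1 promises counts and percentages, item 2's interval for original data may cover each arm's proportion, and Fisher does return p = 1. What is missing is a bound on the between-group difference.

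Nor is it shown that the non-intubated groups cannot do better. Group 1's 11/11 is compatible with a true completion rate as low as 71.5%. A ceiling is likely, not proven.

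The N/A footnote describes the first 29 patients and is not a rule for the final analysis. It correctly declines to give a p-value. The text to change is items 2 to 4. The choice of interval method could be left to an analysis plan, but the protocol itself assigns completion to ANOVA, so this is stated text and not an omission.

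**Conclusion.** The point holds in a limited form. The tests assigned to completion cannot support the feasibility aim. They give nothing, or p = 1, if every operation is complete, and they leave 25/30 against 30/30 at p = 0.052 with a shortfall of up to 33.6 points still possible. Intervals would give a bounded statement: at best 88.4% per arm and -11.4 points for the difference.

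This rests on counting complete against partially complete or incomplete, on two-arm comparisons, and on 30 evaluable per arm. The undefined-test result also assumes that the remaining 61 operations are all complete.

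A formal non-inferiority margin is not called for. A margin set now would follow 29 known outcomes, all complete, and 30 per group could not exclude a shortfall of 10 points even with full success. The protocol also describes no randomisation. ASA class differs between the groups (p = 0.04, Table I-ii), and mean operation time is 77.4 in group 1 against 37.3 and 39.7 (Table VI). The between-group difference is therefore descriptive.

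**What to change.** In the statistical analysis list, take completion out of item 3 and exempt it from the difference test in item 4. Add in substance:

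*Completion will be reported as the proportion of operations scored complete in each group, with an exact (Clopper-Pearson) 95% confidence interval. Group 2 minus group 1 and group 3 minus group 1 will be given with Newcombe score 95% confidence intervals. Conclusions will rest on the lower limit of these intervals. A non-significant p-value will not be taken as evidence of similarity. The differences are descriptive.*

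Counts at all three completion levels remain under item 1. Separately, reconcile the second-year primary outcome list with the paragraph that makes completion primary, so that it is clear which outcome the final conclusion rests on.

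The cost is a few lines of text, with no new data and no change in numbers. The price is a modest claim: about 11 points at best, and nearer 17 after one non-complete operation in group 3.
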